4.3 Study Hypothesis

The Oxford Acute Myocardial Infarction - Pressure-controlled Intermittent Coronary Sinus Occlusion in STEMI (OxAMI-PICSO) study aims to analyze the potential benefit of PICSO in a selected population of STEMI patients. In patients with pre-stenting high IMR, and thus with larger infarct size and more compromised microvasculature status, PICSO treatment added to the conventional revascularization gold standard is expected to be associated to a better myocardial reperfusion. This will be assessed by measurement of indexes of coronary physiology and by CMR evaluation of indexes associated to infarct size, myocardial salvage and microvascular obstruction, and other biomarkers. The comparator group will be matched participants previously enrolled in the OxAMI study, with STEMI and with a pre-stenting IMR above 40.

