5. OBJECTIVES AND OUTCOME MEASURES/ENDPOINTS

Objectives	Outcome Measures/Endpoints
------------	----------------------------

Primary Objective
 
To assess the impact of PICSO on coronary physiology parameters, on infarct size, on myocardial salvage and on microvascular obstruction at CMR in a selected population of STEMI patients at higher risk of no reflow and with the theoretical prerequisites that make more likely to respond to PICSO treatment. The control group will be represented by a highly matched group of patients from the ongoing Ox-AMI (Oxford Acute Myocardial Infarction) project (Ethics Ref 11/SC/0397), who have undergone all other aspects of the study protocol, including assessment of coronary physiology at 24 hours post primary PCI, 24-48 hours and 6 months CMR, but who have not received PICSO treatment.
	
Area at risk, Infarct size, Myocardial salvage and microvascular obstruction measured by cardiac magnetic resonance at 24-48 hours

Secondary Objectives
 
The OxAMI-PICSO study aims to evaluate the utility of individual biomarkers (blood components derived substances from cells, DNA, plasma etc) in the assessment of coronary artery disease and myocardial infarction. The OxAMI-PICSO may show also how these individual biomarkers may be modified by PICSO treatment.
	
Coronary flow reserve (CFR), Fractional Flow reserve (FFR), index of microcirculatory resistance (IMR) measured at 24 hours after PCI.
 
Infarct size and microvascular obstruction extent measured by cardiac magnetic resonance at 6 months
 
Individual Biomarkers related to coronary artery disease/myocardial infarction at three time points (PCI, 24/48 hours after PCI and 6 months). These include: blood biomarkers of myocardial injury, metabolism and inflammation.

Tertiary Objectives
 
To evaluate the rate of PICSO failure deployment, coronary sinus complications, and additional time and radiation exposure associated to for PICSO deployment
	
Rate of PICSO failure deployment
 
Rate of coronary sinus complications: perforation, dissection, thrombosis
 
Time for PICSO deployment / additional screening time and radiation dose

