7.3. Exclusion Criteria

The participant may not enter the study if ANY of the following are known to apply:

- Patients in whom safety or clinical concerns preclude participation.
- Known anaemia (Hb <9).
- Pregnant or breast feeding females.
- Revascularization by mean of balloon angioplasty without stenting
- History of stroke, TIA or reversible ischemic neurological disease within last 6 months
- Known severe renal failure (eGFR < 30 ml/min/1.73m²) or history of dialysis or renal transplant
- Previous coronary bypass artery grafting
- Known severe valvular abnormalities
- Previous STEMI presentation
- Presentation with cardiogenic shock
- Severe bradycardia (Heart rate < 50 beats per minutes)
- STEMI due to stent thrombosis
- Unconscious on presentation

- Non-cardiac comorbidities and life expectancy < 1 year
- Use of warfarin
- Presence of pacemaker or other electrodes in the coronary sinus
- Contraindications to adenosine
- Additional exclusion criteria for participants undergoing CMR
 - claustrophobia which limits / prevents participants from remaining in CMR scanner.
 - patients who cannot lie flat on the scan table.
 - patients with metallic implants, pacemakers, implantable defibrillators etc, unless known to be CMR compatible.
 - patients with known allergy to medium of contrast (gadolinium)

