8.3 Study timeline (see “Integrated flowchart for OxAMI-PICSO study” as below)

The OxAMI-PICSO study will take place beside an ongoing large prospective observational study in STEMI patients (OxAMI study). Patients fulfilling the OxAMI-PICSO criteria will be invited to participate in the study. OxAMI-PICSO study will constitute of 5 main stages:

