12.2 Analysis of Endpoints

In keeping with our usual practice we will obtain expert statistical advice from the Centre for Statistics in Medicine (or equivalent) for each specific task. Summary statistics, including means, medians, and

variances, will be calculated at each time point and for each type of data (e.g. parameters derived from coronary physiology and CMR). The distribution of the levels will be described. It may be necessary to log transform the data before further statistical analysis. For each parameter an analysis of variance will be carried out at each time point.

Control group in OxAMI-PICSO study is represented by a highly matched group of patients underwent to primary PCI, with a prestenosing IMR > 40 and with available 24 hours recath and 24-48 hours/6 months CMR data. Matching will be performed by application of a propensity score matching analysis including the following predictors in the model: age, sex, pain to wire time, thrombotic burden (assessed as angiographic thrombus score), thrombus aspiration performance, stent volume, glycoprotein IIbIIIa inhibitors adoption.

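### Section 12.2 does not require the historical OxAMI controls to meet the 7.2 age range or the 7.3 exclusions that treated patients must meet, and the propensity model covers none of the 7.3 conditions

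*Combined protocol and SAP*

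**What the plan says.** The controls are described in four places.

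- Section 4.3: "The comparator group will be matched participants previously enrolled in the OxAMI study, with STEMI and with a pre-stenting IMR above 40".
- Section 5, primary objective: OxAMI patients "who have undergone all other aspects of the study protocol, including assessment of coronary physiology at 24 hours post primary PCI", plus the two CMR scans, but without PICSO.
- Section 10.1: historical OxAMI patients, matched by propensity score.
- Section 12.2: a "highly matched group of patients underwent to primary PCI, with a prestenosing IMR > 40 and with available 24 hours recath" and CMR data at 24-48 hours and 6 months. The matching model contains age, sex, pain-to-wire time, thrombus score, thrombus aspiration, stent volume and glycoprotein IIb/IIIa inhibitor use.

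Treated patients must be 30 to 90 years old with STEMI (7.2) and must pass 7.3, which opens with "The participant may not enter the study if ANY of the following are known to apply". That list includes "Previous STEMI presentation", "Presentation with cardiogenic shock", stent thrombosis as the cause of the STEMI, previous bypass surgery, heart rate below 50, recent stroke or TIA, warfarin use and severe valve disease.

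Concurrent patients who do not receive PICSO have no CMR (section 6, stages 4 and 5 in 8.3, Appendix B).

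**The concern.** A comparison with historical controls needs both groups to be drawn under the same eligibility rule before any matching. Here the treated group has a long exclusion list and the plan does not say that the control group has it too. Matching cannot repair this for a trait that is not in the model.

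The trait that matters most is previous STEMI. An old scar could be counted as infarct on the control scans, and section 9.3 refers to published methods without stating a rule for separating old scar from new. Shock, and perhaps stent thrombosis, could plausibly go with larger infarcts. If such patients were present among the controls only, mean control infarct size would rise and PICSO would look better than it is. Because concurrent untreated patients are not scanned, no second comparison in the study could reveal this.

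There is also a point of timing. The controls are historical, so some of their CMR results may already exist when they are chosen. An eligibility rule that is not written down leaves room to settle it after outcomes are known.

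**Working it through.** **Step 1: which 7.3 conditions are already closed off for controls?**

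| 7.3 condition | Closed by the control definition or required data? |
|---|---|
| Claustrophobia, unable to lie flat, incompatible implants | Probably: controls completed CMR |
| Contraindication to adenosine | Probably: a hyperaemic IMR was obtained |
| Severe renal failure (eGFR < 30) | Probably, if control CMR used gadolinium under the guidance cited in 11.8 |
| Balloon angioplasty without stenting | Yes in practice: pre-stenting IMR and stent volume presuppose a stent |
| Cardiogenic shock, unconscious at presentation | Not formally; complete follow-up makes them less likely |
| Previous STEMI, stent thrombosis, previous bypass surgery | No |
| Bradycardia, recent stroke or TIA, warfarin, severe valve disease | No, but the documents give no link to infarct size |

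The 7.2 age range is not stated for controls either. Age is in the propensity model, so this part of the gap is small in practice.

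**Step 2: the plan's own figures.** Section 12.1 gives 12 per group for a 29% reduction at 95% confidence and 80% power, later raised to 25 per arm. No SD or control mean is stated, so the 12 cannot be reproduced. It can only be solved backwards for the coefficient of variation (CV), taking a two-sided 0.05 level and the normal approximation:

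CV = 0.29 × √(12/2) / (1.960 + 0.842) = 0.254.

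The eligibility gap does not depend on this value; it serves only to scale step 4.

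**Step 3: illustration of the bias, with no true device effect.** Let *f* be the share of controls who would fail 7.3 and *r* the ratio of their mean infarct size to that of eligible controls. Both are assumptions; the documents give neither. Setting the eligible mean to 1:

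- control mean = 1 + f(r − 1)
- spurious reduction = f(r − 1) / [1 + f(r − 1)]

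| f | r | Control mean | Spurious reduction | Share of 29% |
|---|---|---|---|---|
| 0 | any | 1 | 0 | 0 |
| 5% | 1.25 | 1.0125 | 1.2% | 4% |
| 10% | 1.5 | 1.05 | 4.8% | 16% |
| 20% | 1.5 | 1.10 | 9.1% | 31% |

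With 25 controls, 10% is two or three patients and 20% is five.

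**Step 4: chance of a significant result favouring PICSO.** The nominal value is 2.5%. With 25 per arm it is Φ( f(r − 1) / [CV × √(2/25)] − 1.96 ), ignoring the small extra variance from mixing two kinds of control.

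| f, r | CV 0.254 | CV 0.5 (assumed) |
|---|---|---|
| 5%, 1.25 | 4% | 3% |
| 10%, 1.5 | 10% | 5% |
| 20%, 1.5 | 29% | 11% |

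**The case against.** The strongest reply is that nobody can show from these documents that the control pool is wider than the treated group. OxAMI's criteria are not given. Section 6 says that OxAMI-PICSO is built on the OxAMI framework, so OxAMI may already carry many of the same exclusions. That stands. A reader might infer a wider pool from section 8.3, where the study runs beside OxAMI and "Patients fulfilling the OxAMI-PICSO criteria will be invited to participate in the study". That sentence says who is invited to OxAMI-PICSO; it is silent on whom OxAMI excludes. For the same reason one cannot say which 7.3 items are peculiar to OxAMI-PICSO.

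Second, section 5 says that the controls underwent all other aspects of the protocol, which could be read to include eligibility. The wording is not exhaustive, but the examples it gives are assessments, and having undergone a procedure is not the same as having met an exclusion list.

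Third, the data requirements do real filtering. This also stands and is reflected in step 1. It leaves previous STEMI, stent thrombosis and previous bypass surgery untouched, since such a patient can be stented, have an IMR above 40 and attend both scans.

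Fourth, the direction of bias is plausible for only a few traits, and the illustrative inputs have no source. Both points stand, and the low case in step 3 is close to nothing.

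**Conclusion.** The omission is real. Followed literally, the stated rule does not bar a control with previous STEMI, stent thrombosis, previous bypass surgery or shock, while a treated patient with the same trait is barred. The propensity model does not cover these traits, and this is the only infarct-size comparison.

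The documents do not support the stronger reading that the control group is in fact broader, or that the result will be biased towards PICSO. If OxAMI applied the same exclusions, the bias from this source is zero. On the assumed inputs shown, it runs from 1.2% to 9.1% against a planned 29%. The change should be made because it settles comparability on the primary endpoint at little cost, not because a bias has been demonstrated. Priority: should be fixed. Confidence: moderate, because OxAMI's criteria cannot be seen.

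**What to change.** In 12.2, state that before matching the control pool is restricted to OxAMI patients who meet 7.2 and have no 7.3 exclusion that can be judged at the time of their PCI. Eligibility is checked from baseline OxAMI and medical records, without reference to CMR values, and the propensity match is then done within that pool. Report how many OxAMI patients each criterion removes.

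The cost is a sentence or two in 12.2, a records check and a somewhat smaller control pool. If OxAMI's exclusions already coincide with 7.3, few or no controls are lost and the report documents that the two groups were eligible on the same terms.

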2. SYNOPSIS

Trial Title	Oxford Acute Myocardial Infarction - Pressure-controlled Intermittent Coronary Sinus Occlusion in STEMI
Internal ref. no. (or short title)	OxAMI-PICSO
Clinical Phase	II
Trial Design	Prospective single centre observational cohort study

Trial Participants	Patients admitted for primary percutaneous coronary intervention for ST elevation myocardial infarction	
Planned Sample Size	75 patients	
Treatment duration	Maximum of 90 minutes	
Follow up duration	6 months	
Planned Trial Period	18 months	
	Objectives	Outcome Measures/Endpoints
Primary	To evaluate the effect of pressure intermittent controlled coronary sinus occlusion on the indexes of coronary physiology and on infarct size in STEMI patients at short and mid term follow up.	To evaluate the effect of pressure intermittent controlled coronary sinus occlusion on infarct size measured at cardiac magnetic resonance after 24-48 hours from revascularization.
Secondary	To evaluate the utility of individual biomarkers (blood components derived substances from cells, DNA, plasma etc) in the assessment of coronary artery disease and myocardial infarction investigating also how these individual biomarkers may be modified by PICS0 treatment.	To evaluate the effect of pressure intermittent controlled coronary sinus occlusion on humoral biomarkers and on the evolution of parameters of coronary physiology at 24 hours and infarct size, microvascular obstruction at cardiac magnetic resonance after 6 months from revascularization.
Safety Endpoint	To evaluate the rate of PICS0 failure deployment, coronary sinus complications, and additional time and radiation exposure associated to for PICS0 deployment	
Device name	Pressure intermittent controlled coronary sinus occlusion (PICS0)	
Device Manufacturer	Miracor Medical System	
Device Classification	Interventional Cardiology	

Protocol version no.	Effective Date	Significant Changes	Previous protocol version no.
2.0	01.04.2015	- Clarification of follow up duration - Clarification for what group of patient CMR follow up is meant	v1.0 13.02.2015
3.0	20.06.2016	- Extension of sample size to 75 patients to achieve a minimum of 25 patients with complete dataset	v2.0 01.04.2015

Protocol version no.	Effective Date	Significant Changes	Previous protocol version no.

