6. TRIAL DESIGN

The OxAMI-PICSO study is a prospective single centre observational cohort study of the use of PICSO in patients presenting for primary PCI for acute myocardial infarction. The OxAMI- PICSO study is based upon the established framework of the OxAMI study (Ethics Ref 11/SC/0397).

Patients, age 30-90, presenting with ST elevation myocardial infarction will be considered for inclusion in the study. Measurement of IMR before stenting is an essential prerequisite for the study: only patients with pre-stenting IMR > 40 will be considered eligible for the PICSO treatment. Patients with IMR≤ 40 will remain in the study but will not undergo PICSO treatment. The procedure for consent in patients undergoing emergency PCI will be as already established in the ongoing OxAMI study, and is discussed below in Section 8.1.2.

The PCI procedure will be undertaken in a standard fashion, and include the use of pressure wire measurements before and after stent deployment. Aspiration or distal protection devices may be used if clinically indicated and where vessel anatomy is suitable. The devices used and the procedural techniques will be driven by clinical decision making at the patient and institutional level, and carried out in accordance with the Oxford University Hospitals NHS Trust (OUHT) departmental guidelines for PCI.

PICSO treatment will be added on top of the conventional treatment.

The protocol will constitute of 5 main stages described in details in the next sections (Section 8.3).

Only patients with pre-stenting IMR > 40 and who assent to receive PICSO treatment will undergo 24 hours coronary angiogram with coronary physiology measurement, 24-48 hours CMR scan and 6 months CMR scan. Patients who assent to participate in the study but in whom the pre-stenting IMR ≤ 40, or those in whom the pre-stenting IMR > 40 but the participant declines PICSO treatment will remain in the study for blood sampling and clinical data collection at the same follow up time points (24 hours, 48 hours and 6 months). A summary of the study design, indicating the time points and procedures, is shown in Section 8.3.

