8.4 Definition of End of Trial

Recruitment to the study will cease as soon as 25 participants have undergone PICSO treatment and have completed follow-up at 6 months. The study will end on the date of the last CMR at 6 months follow up of the last participant recruited.

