12 STATISTICS

12.1 Number of Participants

The OxAMI-PICSO study aims to investigate the potential benefit of PICSO in a highly selected population of STEMI patients. In line with the data reported by Sayeed et al in a previous metanalysis on 7 studies about PICSO application in animal models, the recently published Prepare-RAMSES study also observed a 30% reduction in IS in the treatment arm, however such reduction was not statistically significant in comparison to the control arm [19]. The study, however could still show a benefit of PICSO in terms of IS reduction at six months follow up in the subgroup of patients receiving high PICSO quantity. The study, however, was significantly hampered by the inclusion of relative low risk patients and by a small sample size. The author managed indeed to deliver full PICSO treatment only in 63% of the initial planned cohort (12 patients, of the 30 planned, received a prolonged treatment with PICSO) [22].

In order to address the first limitation of the Prepare-RAMSES study, OxAMI-PICSO study will select patients with a preexisting higher IMR. In this way PICSO is meant to be applied only in a population at higher risk and highly likely to get benefit from its application.

In this regard assuming that the stricter inclusion criteria may allow to detect a substantial benefit from PICSO compared to the control group and expecting that this will allow to achieve a significant 29% reduction in IS as shown in Sayeed's metanalysis [19], we initially calculated a final sample size of 12 patients with complete final data per each group with an interval of confidence at 95% and a 80% power. However considering that this was the final same sample size enrolled in the Prepare-RAMSES study, initially meant to recruit 30 patients per arm, we propose to double the actual sample size from 12 to 25 per arm.

Allowing for participants who do not wish to undergo repeat cardiac catheterisation, or cardiac MRI, we anticipate that approximately 75 patients may be recruited to the study in order to achieve full participation and complete follow up in 25 subjects.

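### Controls must have 24 h re-catheterisation and 6-month CMR data to enter the 24–48 h primary comparison, and no treated analysis set is defined

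*Combined protocol and SAP*

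**What the plan says.** The synopsis sets the primary outcome as "infarct size measured at cardiac magnetic resonance after 24-48 hours from revascularization". The Section 5 outcome list likewise places the primary CMR measures at 24–48 h. It puts 24 h coronary physiology and 6-month CMR among the secondary outcomes. On analysis, Section 12.2 says: "For each parameter an analysis of variance will be carried out at each time point".

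One control group serves all of these. Section 12.2 defines it as matched primary PCI patients "with a prestenosing IMR > 40 and with available 24 hours recath and 24-48 hours/6 months CMR data". Section 5 describes controls as having been through every study assessment other than PICSO, "including assessment of coronary physiology at 24 hours post primary PCI, 24-48 hours and 6 months CMR". Neither section limits the re-catheterisation or 6-month condition to the endpoints that use those data.

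For treated patients there is only planning text. Section 12.1 gives the first sample size thus: "we initially calculated a final sample size of 12 patients with complete final data per each group". It then plans about 75 recruits "in order to achieve full participation and complete follow up in 25 subjects". Section 8.4 says: "Recruitment to the study will cease as soon as 25 participants have undergone PICSO treatment and have completed follow-up at 6 months". These are a sample-size target and a recruitment stop. No section says which treated patients enter which analysis.

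On who is scanned, Section 6 states: "Only patients with pre-stenting IMR > 40 and who assent to receive PICSO treatment will undergo 24 hours coronary angiogram", and it covers both CMR scans in the same sentence. Sections 8.3.4 and 8.3.5 restrict the scans to participants who receive the device. Section 5 lists the rate of failed deployment as an outcome.

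**The concern.** Having a re-catheterisation and a 6-month scan is something that happens, or fails to happen, after baseline. It depends on survival, on how ill the patient is and on willingness to return, and each of these may be related to infarct size. The propensity model in Section 12.2 uses age, sex, pain-to-wire time, thrombus score, thrombus aspiration, stent volume and glycoprotein inhibitor use. Matching on these does not remove selection on later completion.

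The 24–48 h comparison needs neither the re-catheterisation nor the 6-month scan. A control who had a good primary scan and died at three months is nevertheless excluded from it. Whether the matching treated patient would also be excluded is not stated. With historical controls, no randomisation and 25 per arm, leaving that choice until the data have been seen weakens the primary result.

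**Working it through.** **Is the restriction real?** Section 12.2 separates 24–48 h and 6 months with a slash, which alone might be taken as either scan. Section 5 joins the two with *and*, so both are required.

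**What the documents give for sizing it.** They give a 29% reduction, 80% power, 95% confidence, 12 per group at first and then 25 per arm. They give no mean or SD of infarct size, and no completion rate for either arm. The ratio of 75 recruited to 25 complete cannot stand in for one: it concerns recruits to this study, not OxAMI controls, and the documents do not say how many of the 75 would have IMR of 40 or less or decline PICSO.

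**The plan's own figure.** Twelve per group cannot be reproduced without an SD, but the coefficient of variation (CV = SD / control mean) that it implies can be found. With two-sided 5% assumed, n = 2 × (1.960 + 0.842)² × CV² / 0.29². Setting n = 12 gives CV = (0.29 / 2.802) × √6 = 0.254. The planned effect is then 0.29 / 0.254 = 1.14 SD. The standard error of a difference at 25 per arm is √(2/25) = 0.283 SD.

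**Case A: only controls are filtered (all inputs assumed).** Let standardised infarct size be z ~ N(0,1) and P(complete) = 1 / (1 + exp(−(a + b·z))), with a solved for the stated completion rate. The shift is the mean of z among completers. Its absolute size in SD is:

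| Completion | b = 0.3 | b = 0.6 | b = 0.9 |
|---|---|---|---|
| 70% | 0.088 | 0.168 | 0.234 |
| 80% | 0.059 | 0.113 | 0.160 |
| 90% | 0.030 | 0.058 | 0.083 |

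The sign follows b. If patients with larger infarcts are less likely to complete, the control mean is too low and PICSO looks worse. If well patients are the ones who decline later visits, the control mean is too high and PICSO looks better. Against the standard error, the shifts are 0.030 / 0.283 = 0.11, 0.113 / 0.283 = 0.40 and 0.234 / 0.283 = 0.83. Against the planned 1.14 SD, they are about 3%, 10% and 20%.

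**Case B: both arms are filtered, with the same a and b.** With no true effect the two shifts are equal and the bias is zero. With a true effect of 1.14 SD, the control shift minus the treated shift lies between −0.008 SD (90%, b = −0.3) and −0.156 SD (70%, b = +0.9). It is towards the null at every point of the grid, for either sign of b.

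**Data given up.** If 25 controls remain after a filter that keeps 70–90%, there were 25/0.9 = 28 to 25/0.7 = 36 before it. If only the control arm grew to that size, the standard error would fall by 1 − √((1/25 + 1/n) / (2/25)), which is 2.7% at n = 28 and 8.0% at n = 36. Under 1:1 matching n stays at 25 and the gain is a larger pool to match from.

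**Who is scanned.** Consider a patient with IMR above 40 who assents but in whom the device cannot be deployed. Section 6 names only patients with IMR of 40 or less and decliners as going without the scans, which suggests that this patient is scanned. Read literally, Sections 8.3.4 and 8.3.5 suggest not. Appendix A is headed for the PICSO group and does not settle it.

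**The case against.** The best defence is that one cohort with complete physiology and both scans fits the stated primary objective. In the synopsis and Section 5 that objective covers coronary physiology as well as infarct size, and the synopsis adds short- and mid-term follow-up. A common cohort is also easier to match once and to describe. This stands as a reason to keep the complete-data cohort. It does not justify making that cohort the only one for a primary outcome fixed at 24–48 h, when the outcome lists place 24 h physiology and 6-month CMR as secondary.

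Second, the planning text in Sections 12.1 and 8.4 points to complete data in both arms. That is fair, and it makes Case B the more likely intention. A reader might infer instead that the filter is one-sided and flatters PICSO. The documents do not support this: they do not say that treated patients without later data are analysed, and under a one-sided filter the direction is open. Equally, a sample-size target does not define an analysis set, so one-sided selection is not ruled out.

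Third, a reader might take Sections 6 and 8.3.4/8.3.5 as contradicting each other. That is too strong. The Section 6 sentence can be read as a necessary condition that the later sections narrow, Section 8.3.4 says the assessments may be done, and none of the three mentions failed deployment.

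**Conclusion.** The control-entry rule is broader than the primary comparison needs, and the treated analysis set is undefined. Both are established from the text. The consequence depends on an unstated choice: one-sided selection with bias in either direction, or a completer analysis in both arms that is roughly unbiased, or conservative, but discards primary data and applies only to completers. The cancellation in the second case assumes that completion depends on infarct size in the same way in both arms.

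The size is illustrative only. The controls-only shift of 0.03–0.23 SD, about 0.11 SD mid-range, rests on assumed completion rates and slopes, and the documents fix neither the size nor the sign. A combined figure that adds a guess for unscanned failed deployments would stack assumptions and should not be quoted.

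The point should be settled before analysis because it bears on the primary comparison and costs little. The scan wording is a minor ambiguity.

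**What to change.** 1. In Section 12.2 and the Section 5 control description, make eligibility endpoint-specific. For the 24–48 h comparison, require only pre-stenting IMR above 40 and a 24–48 h CMR. Apply the re-catheterisation condition to the 24 h physiology endpoint and the 6-month CMR condition to the 6-month endpoint.
2. State that every PICSO patient with a 24–48 h CMR enters that comparison, whether or not later data exist.
3. Keep the cohort with complete data in both arms as a sensitivity analysis. Report how many OxAMI patients with IMR above 40 and a 24–48 h scan lack each later assessment.
4. Reconcile Section 6 with Sections 8.3.4 and 8.3.5 on whether a failed deployment has the study CMR, and define what counts as receiving the device. Name before analysis whether the primary treated set is all assenters or device recipients. A full all-assenters result is available only if failed deployments are scanned.

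The cost is mainly wording. Control sets may differ between endpoints and a separate propensity match may be needed for each, so the single common cohort survives only as the sensitivity analysis. Under 1:1 matching the gain is a larger pool of controls, not a larger sample.
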